STUDY IDENTIFICATION

Bioanalytical Laboratory for 6β-Hydroxycortisol and Free Cortisol Analyses	To be provided	ed separately, if applicable
Statistician	PPD Covance Tel: PPD Email: PPD	MSc
Medical Writer	PPD Covance Tel: PPD Email: PPD	PhD

SYNOPSIS

Study Title

A Phase 1, Open-label, Two-part, Fixed-sequence Drug Interaction Study to Investigate the Effect of Strong CYP3A4 Inhibitor (Itraconazole) and CYP3A4 Inducer (Rifampin) on the Pharmacokinetics of LOXO-305 in Healthy Adult Subjects

Objectives

The primary objectives of the study are:

- to assess the impact of multiple oral doses of itraconazole (a strong cytochrome P450 [CYP]3A4 and P-glycoprotein [P-gp] inhibitor) on the single oral dose pharmacokinetics (PK) of LOXO-305 in healthy adult subjects;
- to assess the effect of multiple oral doses of rifampin (strong CYP3A4 inducer) on the single oral dose PK of LOXO-305 in healthy adult subjects;
- to assess the effect of a single oral dose of rifampin on the single oral dose PK of LOXO-305 in healthy adult subjects.

The secondary objectives of the study are:

- to assess the safety and tolerability of a single oral dose of LOXO-305 when administered alone and co-administered with multiple oral doses of itraconazole;
- to assess the safety and tolerability of a single oral dose of LOXO-305 when administered alone and co-administered with single and multiple oral doses of rifampin.

Study Design

This is a Phase 1, 2-part study. Each part will be conducted as an open-label, 2-period, fixed-sequence study. Following completion of the sentinel subjects in Part 1, the study parts may be conducted concurrently.

In Part 1, a single oral dose of 200 mg LOXO-305 will be administered in the morning on Day 1 of Period 1, following a fast of at least 10 hours prior to and 4 hours after dosing. Blood samples for PK analysis of LOXO-305 alone will be taken up to 168 hours postdose on Day 1. In Period 2, multiple oral doses of 200 mg itraconazole will be administered twice daily (BID) on Day 8, and once daily (QD) from Day 9 until Day 18 inclusive (for a total of 11 consecutive days). and co-administered with a single oral dose of 200 mg LOXO-305 on Day 12 under fasted conditions. On Day 8, when itraconazole is administered BID, the morning dose will be administered alone at the actual time of the Day 1 LOXO-305 dose (\pm 1 hour), approximately 30 minutes after starting a standard breakfast, and the evening dose will be administered and evening meal. All meals should be entirely consumed within 30 minutes. On Days 9 to 11 and Days 13 to 18, the QD dose of itraconazole will be administered alone at the actual time of the start of a standard breakfast, which should be entirely consumed within 30 minutes after the start of a standard breakfast, which should be entirely consumed within

30 minutes. On Day 12, a single oral dose of 200 mg LOXO-305 and a single oral dose of 200 mg itraconazole will be co-administered in the morning, following a fast of at least 10 hours prior to and 4 hours after dosing with LOXO-305 and itraconazole. Blood samples for PK analysis of LOXO-305 in the presence of itraconazole will be taken up to 168 hours postdose of the LOXO-305 dose on Day 12.

In Part 2, a single oral dose of 200 mg LOXO-305 will be administered on Day 1 of Period 1 following a fast of at least 10 hours prior to and 4 hours after dosing. Blood samples for PK analysis of LOXO-305 alone will be taken up to 168 hours postdose on Day 1. In Period 2, multiple oral doses of 600 mg rifampin will be administered QD from Day 8 until Day 23 inclusive (for a total of 16 consecutive days). On Days 8 and 17, a single oral dose of 600 mg rifampin will be co-administered with a single oral dose of 200 mg LOXO-305 in the morning following a fast of at least 10 hours prior to and 4 hours after dosing with LOXO-305 and rifampin. On Days 9 to 16 and 18 to 23, the dose of rifampin will be administered alone at the actual time of the Day 1 LOXO-305 dose (± 1 hour), following a fast of at least 8 hours prior to and 2 hours after dosing. Blood samples for PK analysis of LOXO-305 in the presence of rifampin will be taken up to 24 hours after the LOXO-305 dose on Day 8 and up to 168 hours after the LOXO-305 dose on Day 17.

Urine samples will be collected on Days 8, 11, 15, and 17 of Part 2 (and may be stored for future potential assessment of 6β -hydroxycortisol and free cortisol concentrations to evaluate the level of CYP3A enzyme induction and/or for further exploratory analysis).

In Part 1, there will be a washout period of 7 days between the dose of LOXO-305 on Day 1 (Period 1) and the first dose of itraconazole on Day 8 (Period 2).

In Part 2, there will be a washout period of 7 days between the dose of LOXO-305 on Day 1 (Period 1) and the first dose of rifampin and dose of LOXO-305 on Day 8 (Period 2).

To assess their eligibility to enter the study, potential subjects will be screened within 28 days (Days -29 to -2) and be admitted to the Clinical Research Unit (CRU) on Day -1 (Check-in).

Subjects will be confined at the CRU from the time of Check-in (Day -1) until End of Treatment (EOT) on Day 19 in Part 1 or Day 24 in Part 2, following completion of all PK and safety assessments or Early Termination (ET) if the subject discontinues. A follow-up phone call will occur for all subjects who received at least 1 dose of study drug (including subjects who are terminated early) 7 days (\pm 2 days) after EOT or ET.

Replacement subjects may be enrolled only if deemed necessary by the Sponsor.

In this study, physical examinations, 12-lead electrocardiograms (ECGs), vital signs, How Do You Feel? (HDYF?) inquiries, clinical chemistry panel, coagulation parameters, CK, complete blood count (CBC), urinalysis (UA; Appendix 2) and concomitant medication recording will be performed at Screening and at specified times during the study (for specific timepoints and details on each study variable, refer to Appendix 4). Adverse events (AEs) and serious adverse events (SAEs) will be collected beginning at informed consent. Adverse events will be reported throughout the study (ie, from signing of the Informed Consent Form [ICF] until End of Study [EOS], or until ET if the subject discontinues from the study and does not complete a follow-up phone call), either as subject medical history (if the event is reported as beginning prior to signing of the ICF or if the event occurs prior to study drug

administration on Day 1 and is assessed as not related to study procedures by the Investigator [or designee]) or as AEs (if the event occurs after signing of the ICF but prior to study drug administration on Day 1 and is assessed as related to study procedures by the Investigator [or designee], or if the event occurs after study drug administration on Day 1 through EOT or ET regardless of relationship to study drug). From EOT or ET through EOS, only AEs assessed as related to study drug by the Investigator (or designee) are to be reported. All SAEs that develop from the time of ICF signing until EOS (or ET, if the subject discontinues from the study and does not complete a follow-up phone call) are to be reported. Study completion is defined as the time of the last subject's follow-up phone call.

Number of Subjects

24 healthy adult male and female subjects (women of non-childbearing potential only); 12 subjects in Part 1 and 12 subjects in Part 2 to ensure that 20 subjects complete the study. This is a phase 1 study and the sample size is not based upon any formal power calculations but is consistent with previous studies of a similar design.

Each subject will participate in either Part 1 or Part 2, but not both.

Every attempt will be made to enroll at least 3 subjects of each sex in the study.

If subjects are withdrawn by the Investigator (or designee) or voluntarily withdraw prematurely from the study, replacement subjects may be enrolled only if deemed necessary by the Sponsor.

Main Criteria for Inclusion

Male subjects and female subjects of non-childbearing potential, between 18 and 55 years of age, inclusive, at Screening, and within body mass index (BMI) range 18.0 to 32.0 kg/m², inclusive. Subjects will be in good general health, based on medical history, physical examination findings, vital signs, 12-lead electrocardiogram (ECG), or clinical laboratory tests at Screening and/or Check-in (Day -1), as determined by the Investigator (or designee).

Investigational Medicinal Products, Dose, and Mode of Administration

LOXO-305 will be supplied by the Sponsor as 100-mg tablets for oral administration. Itraconazole will be supplied by Covance as 100-mg capsules for oral administration. Rifampin will be supplied by Covance as 300-mg capsules for oral administration

Part 1 (CYP3A4 and P-gp Inhibitor):

- Day 1 (Period 1): single oral dose of 200 mg LOXO-305 (2 × 100-mg tablets) following a fast of at least 10 hours prior to and 4 hours after the LOXO-305 dose;
- Day 8 (Period 2): BID dose of 200 mg (2 × 100-mg capsules) itraconazole; the morning dose administered alone at the actual time of the Day 1 LOXO-305 dose (± 1 hour), approximately 30 minutes after starting a standard breakfast, and the evening dose administered approximately 10 (±1) hours after the morning dose, approximately 30 minutes after starting a standard evening meal. All meals should be entirely consumed within 30 minutes;

- Days 9 to 11 and Days 13 to 18 (Period 2): QD oral doses of 200 mg itraconazole administered at the actual time of the Day 1 LOXO-305 dose (± 1 hour), approximately 30 minutes after the start of a standard breakfast, which should be entirely consumed within 30 minutes;
- Day 12 (Period 2): single oral dose of 200 mg LOXO-305 and single oral dose of 200 mg itraconazole co-administered in the morning following a fast of at least 10 hours prior to and 4 hours after dosing.

Part 2 (CYP3A4 Inducer):

- Day 1 (Period 1): single oral dose of 200 mg LOXO-305 (2 × 100-mg tablets) following a fast of at least 10 hours prior to and 4 hours after the LOXO-305 dose;
- Days 8 and 17 (Period 2): single oral dose of 200 mg LOXO-305 and single oral dose of 600 mg rifampin (2 × 300-mg capsules) co-administered in the morning following a fast of at least 10 hours prior to and 4 hours after dosing;
- Days 9 to 16 and Days 18 to 23 (Period 2): QD oral doses of 600 mg rifampin administered at the actual time of the Day 1 LOXO-305 dose (± 1 hour) following a fast of at least 8 hours prior to and 2 hours after the rifampin dose.

All study drugs will be administered with approximately 240 mL of water. An additional 100 mL of water may be administered if needed.

In Part 1, there will be a washout period of 7 days between the dose of LOXO-305 on Day 1 (Period 1) and the first dose of itraconazole on Day 8 (Period 2).

In Part 2, there will be a washout period of 7 days between the dose of LOXO-305 on Day 1 (Period 1) and the first dose of rifampin and dose of LOXO-305 on Day 8 (Period 2).

Duration of Subject Participation in the Study:

Planned Study Conduct Duration: approximately 90 days.

Screening Period:

Planned Enrollment/Screening Duration: up to 28 days (Day -29 to Day -2).

Length of Confinement:

Part 1: a total of 20 days (19 nights), from the time of Check-in (Day -1) through the 168-hour (post-Day 12) PK blood draw and EOT assessments (Day 19).

Part 2: a total of 25 days (24 nights), from the time of Check-in (Day -1) through the 168-hour (post-Day 17) PK blood draw and EOT assessments (Day 24).

Follow-up Phone Call (End of Study [EOS]): 7 days (± 2 days) after EOT or ET.

Criteria for Evaluation:

Pharmacokinetics:

In Part 1, serial PK blood samples for the analysis of plasma concentrations of LOXO-305 will be collected from predose through 168 hours postdose following administration of LOXO-305 alone on Day 1 (Period 1) and with itraconazole on Day 12 (Period 2). In Part 2, serial PK blood samples for the analysis of plasma concentrations of LOXO-305 will be collected from predose through 24 hours postdose following administration of LOXO-305 and rifampin on Day 8 (Period 2) and from predose through 168 hours postdose following administration of LOXO-305 alone on Day 1 (Period 1) and with rifampin on Day 17 (Period 2).

The following PK parameters will be calculated whenever possible, based on the plasma concentrations of LOXO-305 (as appropriate): area under the concentration-time curve from Hour 0 to 24 hours postdose, as calculated by the linear trapezoidal method (for Day 1 and Day 8 of Part 2 PK only [AUC₀₋₂₄]), area under the concentration-time curve from Hour 0 to the last measurable concentration (AUC_{0-t}), area under the concentration-time curve extrapolated to infinity (AUC_{0-inf}), extrapolation for area under the concentration-time curve (%AUC_{extrap}), maximum observed plasma concentration (C_{max}), time to maximum observed concentration (t_{max}), apparent terminal elimination rate constant (λ_Z), apparent systemic clearance (CL/F), apparent first order terminal elimination rate constant (Kel) calculated from a semi-log plot of the plasma concentration versus time curve. The parameter will be calculated by linear least squares regression analysis using the maximum number of points in the terminal log linear phase (eg, 3 or more non-zero plasma concentrations [Kel]), and apparent terminal elimination half-life (t₂).

No value for Kel, AUC_{0-inf}, CL/F, or t¹/₂ will be reported for cases that do not exhibit a terminal log linear phase in the concentration-time profile. The PK sampling to 24 hours on Day 8 in Part 2 may not be sufficient for calculation of several Kel-dependent PK parameters.

No PK parameters will be calculated for subjects with 2 or fewer consecutive timepoints with quantifiable concentrations.

Individual and mean plasma concentration-time curves (both linear and log linear) will be included in the final report.

Safety:

Safety and tolerability will be assessed by monitoring AEs, performing physical examinations and clinical laboratory tests, measuring vital signs, and 12-lead ECGs.

Statistical Methods

Pharmacokinetics:

A mixed effect model including treatment as a fixed effect and subject as a random effect will be used to analyze the natural log (ln)-transformed PK parameters (AUC_{0-t}, AUC_{0-inf}, and C_{max}). The ratios and their 90% confidence intervals (CIs) of the PK parameter for each

treatment comparison will be constructed using the exponentiation of the difference and the CIs from the mixed effect model.

Safety:

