levels, as judged by the Investigator or designee and confirmed by the Sponsor. The Investigator (or designee) should use appropriate judgment in ordering additional tests as necessary to monitor the resolution of events. The Sponsor may request that additional safety tests be performed.

Subjects will receive a follow-up phone call 7 days (\pm 2 days) after EOT or ET to determine if any SAE or drug-related AE has occurred since the EOT or ET visit.

At all times, a subject may be required to remain at the CRU for longer at the discretion of the Investigator (or designee).

Any event that meets the criteria of a suspected unexpected serious adverse reaction (SUSAR) will be reported to the Institutional Review Board (IRB)/Independent Ethics Committee (IEC) according to CRU policy by the Investigator (or designee) and to regulatory authorities by the Sponsor (or Sponsor designee) according to regulatory authority requirements. Refer to Reference Safety Information in the current IB¹ for LOXO-305 for expected adverse reactions.

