- j. On Day 8, BID doses of itraconazole will be administered. On Days 9 to 18 (inclusive), QD doses of itraconazole will be administered. On Day 12, itraconazole will be co-administered with LOXO-305 in the morning following a fast of at least 10 hours prior to and 4 hours after dosing with LOXO-305 and itraconazole. On Day 8, when itraconazole will is administered BID, the morning dose will be administered alone at the actual time of the Day 1 LOXO-305 dose (± 1 hour), approximately 30 minutes after starting a standard breakfast, and the evening dose will be administered approximately 10 (±1) hours after the morning dose, approximately 30 minutes after starting a standard evening meal. On Days 9 to 11 and Days 13 to 18, the QD dose of itraconazole will be administered alone at the actual time of the Day 1 LOXO-305 dose (± 1 hour), approximately 30 minutes after the start of a standard breakfast. All meals should be entirely consumed within 30 minutes.

- 1. Clinical chemistry panel including CK (fasted at least 8 hours), coagulation parameters, CBC, and UA will be performed at Screening, Check-in (Day -1), Days 4 and 7, and Days 11 and 15 (before itraconazole dosing), and at EOT (Day 19) or ET.
- m. Hemoglobin A1c test performed at Screening only.
- n. Alcohol breath test and drugs of abuse urine test, including cotinine. Results from the alcohol and drug tests will be used to determine subject eligibility per the inclusion/exclusion criteria.
- Prior and concomitant medication administration will be recorded beginning at informed consent. In addition, all Investigator-approved medications taken by a subject within 30 days prior to study drug administration for prescription medications, and 14 days prior to study drug administration for non-prescription medications, will be recorded on the subject's electronic Case Report Form.
- p. Female subjects only.
- q. Post-menopausal female subjects only.
- r. EOT is defined as when the subject is released from the CRU following completion of all assessments through Day 19. ET is defined as when the subject is released from the CRU if the subject terminates the study early. Vital signs, ECG, and safety laboratory results for clinical chemistry, hematology, coagulation, and UA are to be available for review by the Investigator or designee prior to subject release from the CRU at the EOT or ET visit.

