8.6. Safety and Tolerability Assessments

8.6.1. Adverse Events

All AEs will be coded using the Medical Dictionary for Regulatory Activities (MedDRA) Version 22.1. All AEs will be assigned severity grade using National Cancer Institute Common Terminology Criteria for Adverse Events (CTCAE) Version 5.0.

A treatment-emergent adverse event (TEAE) will be defined as an AE that starts during or after the first dose, or starts prior to the first dose and increases in severity after the first dose.

A treatment-related TEAE will be defined as a TEAE with a relationship of related to the study treatment (LOXO-305 or itraconazole or rifampin), as determined by the investigator.

For Part 1 of this study, the assignment of TEAEs to the associated treatments will be as follows:

- A TEAE occurring during or after Day 1 dosing and prior to Day 8 dosing will be assigned to 200 mg LOXO-305
- A TEAE occurring during or after Day 8 dosing and prior to Day 12 dosing will be assigned to 200 mg itraconazole
- A TEAE occurring during or after Day 12 dosing will be assigned to 200 mg LOXO-305 and/or 200 mg itraconazole

For Part 2 of this study, the assignment of TEAEs to the associated treatments will be as follows:

- A TEAE occurring during or after Day 1 dosing and prior to Day 8 dosing will be assigned to 200 mg LOXO-305
- A TEAE occurring during or after Day 8 dosing will be assigned to 200 mg LOXO-305 and/or 600 mg rifampin

All AEs will be listed. In addition to the data recorded in the database, the listings will include derived onset time and duration. Onset time will be calculated from the time of the last dose for TEAEs only.

The frequency of subjects with TEAEs and the number of TEAEs will be summarized for the following categories:

- TEAEs (overall, serious, and leading to discontinuation) by treatment
- TEAEs by severity and treatment

- Treatment-related TEAEs (overall, serious, and leading to discontinuation) by treatment
- Treatment-related TEAEs by severity and treatment

The frequency of subjects will be summarized separately for TEAEs and treatment-related TEAEs by the following:

- System organ class, preferred term, and treatment
- Preferred term and treatment
- System organ class, preferred term, day of onset, and treatment

For the AE data the following rules will apply:

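### After early termination, non-serious AEs judged unrelated are no longer collected, so all-cause TEAE tables can slightly undercount subjects who leave soon after a LOXO-305 dose

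*Protocol*

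**What the plan says.** The AE rule appears in the protocol synopsis, 3.1.3, 7.2.1 and Appendix 4 footnote h (both parts), and in SAP 4.3. A post-dose event is an AE "if the event occurs after study drug administration on Day 1 through EOT or ET regardless of relationship to study drug". After that point the rule narrows: "From EOT or ET through EOS, only AEs assessed as related to study drug by the Investigator (or designee) are to be reported". Serious events are exempt: "All SAEs that develop from the time of ICF signing until EOS" are reportable, stopping at ET only if the subject discontinues and the call is not completed.

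Appendix 4 (footnote r in Part 1, s in Part 2) fixes the cut-off for leavers: "ET is defined as when the subject is released from the CRU if the subject terminates the study early". For completers, EOT is Day 19 in Part 1 and Day 24 in Part 2, after the 168-hour sample that follows the Day 12 or Day 17 dose.

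The call is made "7 days (± 2 days) after EOT or ET". Protocol 7.2.1 gives its purpose as "to determine if any SAE or drug-related AE has occurred since the EOT or ET visit", and Appendix 4 footnotes s (Part 1) and t (Part 2) agree. The Appendix 4 grid schedules the HDYF? inquiry, AE/SAE review and medication review at that call.

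SAP 8.6.1 lists "TEAEs (overall, serious, and leading to discontinuation) by treatment", with treatment-related TEAEs tabulated separately. It sets no end to the last assignment window in either part and says nothing about shortened observation.

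**The concern.** One sentence treats EOT and ET as the same kind of milestone, but they differ in time since the last LOXO-305 dose. For a completer the related-only filter starts a full week after dosing. For a subject who leaves it can start within a day. The same non-serious event, at the same time after dose and judged unrelated, is counted in a completer and never recorded in an early leaver.

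The loss occurs at collection, so no later analysis can recover it. Both groups then enter the same all-cause incidence columns, which serve the secondary safety objective with 12 subjects per part. The gap is separate from the case where the call is missed, because completing the call does not lift the filter.

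**Working it through.** **Completer window (protocol day numbers).** Part 1: (19 − 12) × 24 = 168 h. Part 2: (24 − 17) × 24 = 168 h. Both match the stated 168 hours. The Day 1 dose to Day 8 is also 7 × 24 = 168 h in each part.

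**All-cause hours lost for release t hours after the dose: 168 − t.**

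| t (h) | Hours lost | Share of 168 h |
|---|---|---|
| 12 | 156 | 93% |
| 24 | 144 | 86% |
| 48 | 120 | 71% |
| 72 | 96 | 57% |
| 84 | 84 | 50% |
| 120 | 48 | 29% |

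More than half is lost for any release before 84 h.

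**Expected subjects missed.** The plan enrols 24 so that 20 complete, which allows for 24 − 20 = 4 non-completers. The documents give no AE risks or release times, so these are assumed. Let p be the chance of at least one non-serious, not-related TEAE in 168 h, with constant hazard h = −ln(1 − p)/168, and let d be the number of early leavers. Then

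missed = d × [exp(−h·t) − exp(−168h)] = d × [(1 − p)^(t/168) − (1 − p)].

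Example with d = 1, t = 24, p = 0.5: 0.5^(1/7) − 0.5 = 0.906 − 0.5 = 0.41.

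| d | t (h) | p = 0.1 | p = 0.3 | p = 0.5 |
|---|---|---|---|---|
| 1 | 24 | 0.09 | 0.25 | 0.41 |
| 1 | 72 | 0.06 | 0.16 | 0.24 |
| 2 | 24 | 0.17 | 0.50 | 0.81 |
| 2 | 72 | 0.11 | 0.32 | 0.49 |
| 4 | 24 | 0.34 | 1.00 | 1.62 |
| 4 | 72 | 0.22 | 0.63 | 0.97 |

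The d = 4, t = 24 row puts all the allowed non-completers in one column at 24 h. It is an upper extreme: 1.62/12 = 13.5 percentage points.

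**Spreading the release times.** Take Part 1 with 2 early leavers, release uniform over Day 1 to Day 19 (18 days, of which 7 follow Day 12), and a 50% risk of any TEAE in 168 h.

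- No post-ET AE rated related: average loss per leaver after Day 12 = (1 − 0.5)/ln 2 − 0.5 = 0.221. Column loss = 2 × (7/18) × 0.221 = 0.17 subjects of 12.
- Half rated related (recorded hazard halved after ET): √0.5 × (1 − √0.5)/(0.5 × ln 2) − 0.5 = 0.098. Column loss = 2 × (7/18) × 0.098 = 0.08.

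Placing both leavers at 24 h instead gives 2 × (0.5 − 0.094) = 0.81 and 2 × (0.5 − 0.327) = 0.35.

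**Part 2 Day 8.** The next LOXO-305 dose is (17 − 8) × 24 = 216 h later. SAP 8.6.1 pools everything from Day 8, which for completers spans (24 − 8) × 24 = 384 h. The 168 h comparison does not describe this dose.

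**Can the existing call close the gap?** For ET at 24 h the call falls at 24 + 120 = 144 h to 24 + 216 = 240 h after the dose, nominally 192 h. For ET at 48 h or later it falls at 168 h or beyond. Only a release before 48 h with an early call leaves a shortfall, which is up to 24 h for ET at 24 h.

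**The case against.** The strongest reply is that little is lost. SAEs, related AEs and anything starting before release are kept. With a completed call, the serious and treatment-related tables are not cut by this rule. A subject who leaves because of an AE already counts as having a TEAE, so the any-TEAE subject count loses nothing if that event sits in the same column. All this stands. It does not protect the number of TEAEs or the preferred-term tables, where a second, later event can still be missing.

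The Appendix 1 causality definitions also matter. Not related requires timing that rules out a causal link and another suspected cause, which is hard to meet within days of a dose. Related requires that no other cause can be identified. An event with plausible timing and an alternative explanation fits neither, so the share filtered out is uncertain. A missing relationship is counted as related under SAP 8.6.1.

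The windows are not fully like for like. A completer's 168 h includes six further daily doses of itraconazole or rifampin (Days 13–18 or 18–23), while a leaver is off treatment. Constant hazard across both states is a simplification. The Investigator may also delay release, although no minimum stay is set, and safety is descriptive only.

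A reader might infer that co-administration is made to look better tolerated. The documents do not establish this. In Part 1 the LOXO-305-alone and co-administration columns each cover 7 days, with itraconazole alone as a separate column between them, so uniform release times give equal expected loss in each. The inference is more plausible in Part 2, where the pooled group runs from Day 8 to Day 24, but release times there are unknown too.

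**Conclusion.** The gap is real and minor. After ET, non-serious AEs judged not related are not collected even when the call is completed, and SAP 8.6.1 does not allow for the shorter window. All-cause TEAE tables can therefore undercount early leavers in whichever column they leave.

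The likely size is a fraction of a subject per 12: about 0.1 to 0.2 in the Part 1 co-administration column with two leavers at spread-out times, and up to about 1 to 2 subjects if all four allowed non-completers left one column at 24 h. These figures rest on assumed AE risks, release times, related shares and constant hazard. The undercount is possible rather than certain: it needs an early release followed by such an event.

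A reader might also take the rule to mean that only drug-related AEs survive after ET. That is wrong, because SAEs are kept regardless of relationship.

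**What to change.** 1. In the synopsis, 3.1.3, 7.2.1, Appendix 4 footnote h (both parts) and SAP 4.3, limit the related-only rule to the period from EOT to EOS. Add that for subjects who terminate early, all AEs are reported through the follow-up call whatever their relationship.
2. Change the call's stated purpose to match in 7.2.1 and in Appendix 4 footnotes s (Part 1) and t (Part 2). Otherwise the protocol would contradict itself.
3. In SAP 8.6.1, count post-ET events on an all-cause basis up to 168 h after the last LOXO-305 dose. For ET after the Part 2 Day 8 dose, where the completers' window is longer, state the window used and note the shorter observation.

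The cost is wording in two documents and a few more non-serious AE records. No visit or contact is added. Two limits remain: post-ET events rest on recall at one call, which for ET at 24 h may come at 144 h, and leavers are by then off itraconazole or rifampin.
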